4.9 Gaming of the intervention

To assess the extent to which participants 'gamed' the primary outcome i.e. stopped smoking a few days before sample collection, the number and proportion of women who were found to be biochemically verified non-smokers but tested positive for smoking in late pregnancy residual blood samples (where available) will be summarised descriptively by treatment group.

4.10 Cotinine and anabasine test results

For participants who reported as non-smokers and using e/cigarettes or NRT at late pregnancy, the results of the cotinine and anabasine tests will be summarised descriptively, in order to assess the impact of anabasine testing on the derivation of the primary outcome (Table 10). The analysis will be repeated for the 6 months post-partum time point.

4.11 Adverse events

Adverse events related to the study will be presented descriptively by treatment group.

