2.5.3 Adverse events

Serious adverse events (SAEs) that are related to the intervention will be documented. It is not anticipated that the provision of shopping vouchers to women will be associated with any related SAEs.

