2.5.4 Other Collected Data

- *Demographics:* Maternal age, height and weight, household income and ethnicity were collected at baseline.
- Index of Multiple Deprivation (IMD) quintile: The IMD is a measure that ranks each lower layer super output area (LSOA) in order of deprivation, with the most deprived LSOA being ranked the highest. The IMD was derived for each participant by mapping to the participant's postcode. From the IMD the IMD quintile was then derived. A value of 1 represents the most deprived quintile, while 5 represents the least deprived. The postcode used to derive the IMD quintile was collected at baseline.
- The Fagerström Test for Nicotine Dependence (FTND): The FTND is used for assessing nicotine dependence. The test is composed of six questions, the scoring of which is detailed in Appendix 8.1. The FTND was collected at baseline.
- Other smoking information: The age at which the participant started smoking and whether the participant was currently living with someone who smokes were also collected at baseline, along with information on whether the participant used NRT and/or e-cigarettes.

- Antenatal appointment information: The date of the antenatal appointment and the CO reading taken as part of routine care (where available) were collected.
- *EQ-5D-5L:* The EQ-5D-5L was collected as a standardised measure of current health status developed by the EuroQol Group for clinical and economic appraisal. The EQ-5D-5L consists of five questions and a visual analogue scale, each assessing a different quality of life dimension (Mobility, Self-care, Usual activities, Pain/Discomfort and Anxiety/Depression). A weighted and population referenced summary index is derived and will be reported and analysed as part of the health economic analysis.
- Other birth data: Parity and the baby's birth date was collected as well as the status of baby at birth (live/stillbirth).
- Neonatal stay: For babies admitted to neonatal care, length of stay was recorded.
- *Miscarriage data:* Any known occurrence of miscarriage was collected throughout the study duration. The date the event became known to the trial team and date of miscarriage (where available) was collected.

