2.9.3 Follow-up 3: 12 weeks post quit date

For participants in the intervention group who were confirmed quit at four weeks, trial research staff contacted the participant's local SSS eight weeks later to obtain smoking status and CO breath test result as recorded by the SSS. Where this was not available from the SSS, trial research nurses collected this directly from the participant. This information was entered into the trial database. If the CO result was at or below the accepted level for a non-smoker at the site, a £100 voucher was automatically dispatched.

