2.9.4 Follow-up 4: Late pregnancy (34-38 weeks gestation)

All participants were followed up at the primary outcome stage in late pregnancy. Follow-up telephone contact was attempted by the trial contact centre at a random date between 34 and 38 weeks gestation allocated at the time of initial randomisation. Trial research nurses reviewed participants' notes one week prior to the telephone contact to check the health status of mother and baby and alert TCC staff to any adverse events e.g. miscarriage or stillbirth, that required particular sensitivity when conducting follow-up. TCC staff were blind to group allocation.

Three attempts were made by the TCC to contact women. If no contact was established, local research staff followed up women by telephone, text, and letter. On successful contact, women were asked: 'Have you smoked in the last 8 weeks?' If yes, 'Have you smoked more than 5 cigarettes in that time?'. EQ-5D-5L data, and current NRT/electronic cigarette use were also collected at this time point.

Self-report of not smoking was corroborated by cotinine estimation on saliva or urine (when saliva collection could not be tolerated). Where women were using NRT or e-cigarettes, anabasine assay on saliva was also conducted. Cotinine and anabasine were assayed by ABS Laboratories Limited (https://www.acmgloballab.com/about-us/our-locations/europe-london-uk). To minimise the potential for women to 'game' the primary outcome, incentive payments were dependent on the CO result, which is an immediate measure, and not on the cotinine or anabasine level.

An important aspect of the primary outcome for this phase III trial is the proportion of women successfully followed up in both the intervention and control group. To minimise loss to follow-up, particularly among controls, women in both groups will receive Love2Shop vouchers of £50 and £25 for providing data and saliva/urine samples where applicable at the primary (late pregnancy) and secondary (six months post-partum) outcome time points respectively (Figure 2.).

To assess if a) women lost to trial follow-up are still smoking towards the end of pregnancy, and b) the primary outcome has been 'gamed' (saliva cotinine below the cut-off but still smoking in late pregnancy) residual blood from routine late pregnancy samples, where available, will be tested.

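### SAP 2.5.3 and 4.11 define reportable events differently and both keep only related events, while miscarriage and stillbirth have no planned summary by arm

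*SAP*

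**What the plan says.** Section 2.5.3 sets what is recorded: "Serious adverse events (SAEs) that are related to the intervention will be documented". It adds the expectation that there will be none: "It is not anticipated that the provision of shopping vouchers to women will be associated with any related SAEs". Section 4.11 sets what is analysed, in one sentence: "Adverse events related to the study will be presented descriptively by treatment group".

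Pregnancy losses are collected separately. Section 2.5.4 states: "Any known occurrence of miscarriage was collected throughout the study duration". It also lists whether the baby was live or stillborn at birth. Table 3 schedules stillbirth/miscarriage at follow-ups 1 to 4 and at delivery. Section 2.9.4 has nurses review notes a week before the late-pregnancy call so that they can "alert TCC staff to any adverse events e.g. miscarriage or stillbirth".

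Section 2.8 states that participants could not be blinded.

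**The concern.** The recording rule and the analysis rule do not match. One concerns serious events related to the intervention; the other concerns adverse events of any grade related to the study. An analyst cannot tell from the SAP which set goes into the by-arm display.

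Both rules keep only events judged related. Under 2.5.3, an event has to be attributed to an intervention that only one arm is offered, so a by-arm display says almost nothing about whether the arms differ. The losses that could be compared without any judgement of cause are collected, but no by-arm summary of them is planned.

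Losses by arm also help in reading other results. Section 4.5 treats missing birth weight as missing at random given the covariates and does not separate a miscarriage from other missing values; the CACE analysis in 4.8 uses the same outcome. Section 4.4 counts a missing primary outcome as smoking and states no exception for a pregnancy that ended before the late-pregnancy call.

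**Working it through.** **Comparing the text**

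| Item | 2.5.3 | 4.11 |
|---|---|---|
| Type of event | Serious only | Adverse events, no seriousness limit |
| Related to | The intervention | The study |
| Can usual care contribute? | Hardly: no incentives are offered | Yes, in principle: calls, samples and follow-up vouchers apply to both groups (2.9.4) |

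If 2.5.3 decides what enters the database, the wider wording of 4.11 has nothing further to draw on.

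Section 4 and the example tables were then searched for losses. The nearest items are withdrawals with reasons (4.2, split by arm not stated), birth weight (4.5) and length of neonatal stay by group (4.6). Tables 4 to 10 have no row for miscarriage or stillbirth.

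**Whether losses are found equally in both arms**

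Section 2.9.3 describes the 12-week contact only "For participants in the intervention group who were confirmed quit at four weeks". At four weeks, nurse collection of missing CO results is limited to the incentives group (2.9.2). That arm therefore has more occasions on which a loss could become known. The notes review before the late-pregnancy call and the delivery record are not limited to one arm.

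**Size**

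The SAP gives no figure for safety. Its one relevant number is 470 per arm (2.6), which reproduces from 7% against 14%, 90% power, two-sided 5% and 15% loss:

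- Unpooled variance: (1.960 + 1.282)² × (0.07 × 0.93 + 0.14 × 0.86) / 0.07² gives 398 per arm. Then 398 / 0.85 rounds up to 469, or 938 in total.
- Pooled variance: 401 per arm. Then 401 / 0.85 rounds up to 472, or 944 in total.

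Both are close to the stated 940.

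The loss risk p is an assumption, taken as equal in the two arms. Expected losses per arm are 470p. The 95% CI half-width for the risk difference is 1.96 × √(2p(1 − p)/470).

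| Assumed p | Losses per arm | Half-width (points) | Power for a doubling |
|---|---|---|---|
| 0.5% | 2.4 | 0.9 | 14% |
| 1% | 4.7 | 1.3 | 24% |
| 2% | 9.4 | 1.8 | 44% |
| 3% | 14.1 | 2.2 | 60% |
| 5% | 23.5 | 2.8 | 83% |

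As an example with unequal risks, take 2% against 4%: 9.4 against 18.8 losses, SE = √(0.02 × 0.98/470 + 0.04 × 0.96/470) = 0.0111, so a difference of 2.0 points with a 95% CI of about −0.2 to 4.2. A descriptive table with an interval is feasible. A formal test would be weak unless losses were near 5%.

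**The case against.** A reader might infer that the usual-care column is empty by construction. The SAP does not support that. Section 4.11 says study, not intervention, and usual-care women also have study calls, give samples and receive vouchers of £50 and £25 for follow-up data. The display is effectively one-sided only if 2.5.3 governs what is recorded.

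A reader might also infer that losses are never compared. That goes too far. They could surface among the withdrawal reasons in 4.2 or in the CONSORT diagram, whose content is not shown. What can be said is that no by-arm summary of them is planned in the visible text.

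Other points on that side have weight. Which events are recorded is commonly settled in the protocol, to which SAP section 2 refers for full detail. Reporting only related events is a recognisable choice when vouchers are not expected to cause harm. The phrase in 2.9.4 naming miscarriage and stillbirth is about handling calls sensitively and does not define a safety endpoint. The SAP plans no safety test and draws no conclusion of safety.

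These points limit the concern but do not remove it. The mismatch between 2.5.3 and 4.11 lies within the SAP itself. The losses are collected whatever 2.9.4 calls them, and how collected data are summarised is the SAP's business.

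It is also tempting to count only losses confirmed by sources common to both arms. Nothing in the SAP shows that a source is recorded for each loss, and such a rule would drop real events from the incentives arm. It can serve only as a secondary display.

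**Conclusion.** The point holds in a limited form. Two definitions of reportable events are unreconciled. Both filter on relatedness where participants know their allocation, so the by-arm display carries almost no comparative information if 2.5.3 governs. Miscarriage and stillbirth, collected irrespective of relatedness, have no planned by-arm summary.

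The precision figures rest on the planned 470 per arm and on an assumed, equal loss risk between 0.5% and 5%. The consequence is modest: the primary effect estimate does not change, and the comparison would be descriptive. It is worth making because it is cheap.

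**What to change.** 1. Reconcile 2.5.3 with 4.11: state one definition (serious or any grade; intervention or study) and use it in both places.
2. Add to 4.11 a by-arm table over all randomised women, irrespective of relatedness, with rows for miscarriage, stillbirth, live birth and outcome unknown. Give counts, percentages and risk differences with 95% CIs, and no formal test.
3. Count all known post-randomisation losses in this main table. Note beside it that the incentives arm has extra contacts at four and 12 weeks.
4. Where the source of a loss can be identified, repeat the table restricted to losses confirmed by the notes review or the delivery record.
5. List intervention-related SAEs separately.

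The cost is SAP wording and one extra table from data the SAP says are collected, with a restricted repeat where sources allow. Precision will be low. Some losses will lack a date or source, since 2.5.4 records the miscarriage date only where available; their number cannot be judged from the SAP.

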4.12 Planned interim review and analyses

No formal interim analyses will be undertaken.

5 SAP amendment log

Amendment/addition to SAP and reason for change	New version number, name and date
The derivation of biochemically verified smoking status was changed in line with the latest cut-offs advised by ABS laboratories (Table 2).	CPIT III Statistical Analysis Plan_1.1_20210728
A descriptive analysis of cotinine and anabasine results was added (Section 4.10 and Table 10).	
Amendment of analysis of smoking status at 4 weeks, birth weight and sparse data sensitivity analysis to include additional covariates (Sections 4.5, 4.7.1 and 4.8). For all three analyses, whether the outcome was collected before the 16 th March 2020 was included as an additional covariate. For the analysis of birth weight, years of smoking, income status and level of smoking were also included as additional covariates.	

6 Signatures of approval

8.1 Scoring of Fagerström Test for Nicotine Dependence

The Fagerström Test for Nicotine Dependence is scored in the following manner:

- How soon after waking do you smoke your first cigarette?
 - (3) Within 5 minutes
 - (2) 5-30 minutes
 - (1) 31-60 minutes
- Do you find it difficult to refrain from smoking in places where it is forbidden?
 - (1) Yes
 - (0) No
- Which cigarette would you hate to give up?
 - (1) The first in the morning
 - (0) Any other
- How many cigarettes a day do you smoke?
 - (3) 31 or more
 - (2) 21-30
 - (1) 11-20
 - (0) 10 or less
- Do you smoke more frequently in the morning?
 - (1) Yes
 - (0) No
- Do you smoke even if you are sick in bed most of the day?
 - (1) Yes
 - (0) No

The Fagerström score is calculated by adding up the scores from each question, and can take values between 0 and 10. There is no published advice in regards to how to account for missing responses to the Fagerström questionnaire.

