2.6 Sample size

The aim was to recruit 940 participants to the trial (470 per arm). This gave 90% power to detect a doubling of the smoking cessation rate from 7% to 14%, allowing 15% loss to follow-up. The smoking cessation rate in the control group was derived from the smoking cessation rate found in the feasibility trial [2], and two other large trials of smoking cessation interventions in pregnant smokers [3, 4]. The smoking cessation rate in the intervention group was derived from the cessation rate in the feasibility trial, along with considerations of the effect size that would be considered clinically important.

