4.4 Primary outcome analysis

The primary outcome will be analysed using a mixed-effects logistic regression model adjusting for treatment group, age, years of smoking, income status (as measured by the IMD quintile within the participant's nation), level of smoking (as measured by the Fagerström score) and whether the primary outcome was collected before the 16th of March

2020 (the date on which the intervention changed due to the Covid-19 pandemic), with centre as a random effect.

For a small number of participants in Belfast, a biochemical sample was provided but due to a miscommunication with the lab the sample was not analysed for anabasine. It was decided with the TSC that in this scenario, those who self-reported as quit and had a CO reading less less than 4 ppm would be classed as non-smokers for the primary analysis.

If a participant is missing data on the primary outcome, it shall be assumed the participant is smoking, as per the Russell Standard [9]. If a participant is missing data on any covariates to be included in the analysis models, the missing values will be replaced with centre-specific means [10]. The assumptions of the model will be checked. If the assumptions are found to be questionable, the data will be transformed or non-parametric data analysis methods will be used.

It was considered whether sparse data bias would be an issue when conducting the primary analysis [11]. Given the sample size calculation assumption that 7% of participants in the control group would quit, it can be assumed that if the full sample size of 940 are recruited and the intervention has no effect, then the 'event' of a participant quitting smoking at the late pregnancy stage would be expected to occur approximately 66 times during the study. The primary analysis model contains five fixed effect variables, which means approximately 13 events per variable are expected. This exceeds the recommended minimum of 10 events per variable when using logistic regression and as a result it was not considered necessary to use an alternative statistical model [12].

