8.4 Example tables

8.4.1 Baseline characteristics

Table 4: Baseline characteristics for all participants and for participants who provided a cotinine/anabasine verified smoking status at the primary outcome follow-up.

	All randomised participants		Participants a smoking s primary out	who provided status at the come stage
	Control	Intervention	Control	
Height m	(11=)	(11=)	(11=)	(11=)
n (%)				
Mean (SD)				
Weight kg				
n (%)				
Mean (SD)				
BMI, kg/m ²				
n (%)				
Mean (SD)				
Ethnicity, n (%)				
Maternal age at booking, years				
n (%)				
Mean (SD)				
Previous live births				
Median (range)				
Index of multiple				
deprivation, n (%)				
1st quintile (most deprived)				
2nd quintile				
3rd quintile				
4th quintile				
5th quintile (least deprived)				
CO reading at maternity				
booking, ppm				
n (%)				
Mean (SD)				
First cigarette within 5 minutes				
of waking, n (%)				
Within 5 minutes				
5-30 minutes				
31-60 minutes				
Difficulty not smoking in				
Torbidden places, n (%)				
Yes				
NO Missing				
1st cigarette most difficult to				
give up n (%)				
The first in the morning				
Any other				
Missing				
Cigarettes smoked a day, n (%)				
10 or less				
11-20				
21-30				
31 or more				
Missing				
Smoke more frequently in the				
morning, n (%)				

Yes		
No		
Missing		
Smoke even if sick in bed most		
of the day, n (%)		
Yes		
No		
Missing		
Fagerström score		
n (%)		
Mean (SD)		
Partner smokes, n (%)		
Yes		
No		
Missing		
Age at which participant started		
smoking, years		
n (%)		
Mean (SD)		
Uses NRT n (%)		
Yes		
No		
Missing		
Uses e-cigarettes n (%)		
Yes		
No		
Missing		

Table 5: Primary and secondary analyses

	Number of events/Number in group	Adjusted odds ratio (95% Cl)	p-value
Late pregnancy			
Incentives			
Usual care			
Engagement with SSS			
Incentives			
Usual care			
4 week post-quit			
Incentives			
Usual care			
6 months post-partum			
(continuous abstinence)			
Incentives			
Usual care			
6 months post-partum			
(point abstinence)			
Incentives			
Usual care			

Table 6: Comparison by treatment group of self-reported smoking status pre-Covid and post-Covid

	Incentives Pre-Covid Post-Covid		Usual care	
			Pre-Covid	Post-Covid
4 week, n (%)				

	Incentives		Usual care	
	Pre-Covid	Post-Covid	Pre-Covid	Post-Covid
Non-smoker				
Smoker				
12 week, n (%)				
Non-smoker				
Smoker				
Late pregnancy, n (%)				
Non-smoker				
Smoker				
6 months				
post-partum, n (%)				
Non-smoker				
Smoker				

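### The Fagerström key in SAP 8.1 has no zero option for time to first cigarette, so it yields totals of 1 to 10 and contradicts the stated range of 0 to 10

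*SAP*

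**What the plan says.** Section 8.1 of the SAP gives the scoring key for the six Fagerström items. The first item asks "How soon after waking do you smoke your first cigarette" and lists three answers: within 5 minutes (3 points), 5-30 minutes (2 points) and, as the last and lowest, "1) 31-60 minutes". Nothing is listed beyond 60 minutes. Each of the other five items ends in an answer worth 0.

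The section then gives the range of the total: "The Fagerström score is calculated by adding up the scores from each question, and can take values between 0 and 10". On incomplete questionnaires it offers no rule: "There is no published advice in regards to how to account for missing responses to the Fagerström questionnaire".

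Table 4 in Section 8.4.1 has a block for the same item, with a label that begins "First cigarette within 5 minutes". It shows the same three categories and no row for a later first cigarette.

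The score is then used widely. The primary model in Section 4.4 adjusts for "level of smoking (as measured by the Fagerström score) and whether the primary outcome was collected before the 16th of March" 2020. The secondary models (4.5), the Firth model (4.7.1) and the CACE model for birth weight (4.8) also adjust for it, and it defines one of the subgroups in 4.7.3. For missing covariates, Section 4.4 says that "the missing values will be replaced with centre-specific means".

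**The concern.** The key and the stated range cannot both be right. The gap is also more than a wrong limit in a sentence, because one possible answer to the first item has no score at all. Changing the stated range to 1 to 10 would remove the contradiction but would still leave a woman who first smokes after 60 minutes without a category.

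Two programmers working from Section 8.1 could therefore derive different totals for the same woman. The total feeds every adjusted model. The subgroup cut-off is to be taken from the score distribution in the previous CPIT trial, so the total has to be derived in one fixed way over its full range for that cut-off to mean the same thing here. Table 4 as printed also has nowhere to count these women.

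**Working it through.** **1. The stated range.** The inputs are the item scores in Section 8.1: {3,2,1}, {1,0}, {1,0}, {3,2,1,0}, {1,0}, {1,0}.

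- Combinations: 3 × 2 × 2 × 4 × 2 × 2 = 192.
- Minimum total: 1 + 0 + 0 + 0 + 0 + 0 = 1.
- Maximum total: 3 + 1 + 1 + 3 + 1 + 1 = 10.

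The upper limit of 10 is reproduced. The lower limit of 0 is not.

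**2. With a zero added to the first item.**

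- Combinations: 4 × 2 × 2 × 4 × 2 × 2 = 256.
- Minimum total: 0. Maximum total: 10.

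This matches the stated range exactly.

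**3. What could happen to a woman in the unlisted category.** Let S be the sum of her other five items. S runs from 0 to 1 + 1 + 3 + 1 + 1 = 7.

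| Handling of the first item | Total used | Support in the SAP |
|---|---|---|
| Scored 0 | S (0 to 7) | Implied by the stated 0 to 10 range |
| Placed in 31-60 minutes | S + 1 (1 to 8) | Lowest answer that is listed |
| Unscorable, total missing | Centre mean | Section 4.4 rule, if the total counts as missing |

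**4. Size of the third route (illustration only).** The documents do not give the share of women in the unlisted category, so it was varied from 5% to 30%. The other assumptions were:

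- 940 women, with a treatment odds ratio of 2.16, from the 7% and 14% in Section 2.6: (0.14/0.86) / (0.07/0.93) = 2.16;
- mean totals of about 0.6 in the unlisted group and 4.2 in the rest;
- a change in log odds of quitting of -0.25 per Fagerström point;
- a single-level logistic model with treatment and score only, and replacement by one overall mean, since centres were not modelled;
- 300 simulated trials per row.

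| Share unlisted | Treatment log OR, true score | Treatment log OR, mean replaced | Shift | SE, true score | Shift / SE | Fagerström coefficient, true to replaced |
|---|---|---|---|---|---|---|
| 5% | 0.784 | 0.778 | 0.006 | 0.224 | 0.03 | -0.258 to -0.244 |
| 15% | 0.769 | 0.757 | 0.012 | 0.215 | 0.06 | -0.255 to -0.223 |
| 30% | 0.781 | 0.761 | 0.020 | 0.204 | 0.10 | -0.250 to -0.190 |

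Under these assumptions each affected woman's score rises on average by 4.2 - 0.6 = 3.6 points. The one-point route was not simulated. Scoring 0 causes no error.

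**The case against.** **This is an appendix omission that the SAP itself resolves.** A total of 0 is possible only if the first item can score 0, so the intended score can be recovered from the stated range, and the scoring code may already be right. This stands in large part: scoring 0 is at least as likely as either other route. It does not remove the defect, because the key is the stated derivation and it is incomplete.

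**A line may have been lost when the PDF was read.** The text of Table 4 is visibly damaged, and its block for this item also lacks the row for missing answers that the other five items have. This cannot be excluded. It is unlikely, because the same category would have had to disappear from two separate places with different layouts. The absent row for missing answers in an example table carries no weight by itself.

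**A stronger reading is tempting but unsupported.** A reader might infer that the least dependent women will be given their centre's average dependence in the primary model. That needs three steps the SAP does not state: that this answer is stored as missing, that one unscored item makes the total missing, and that Section 4.4 then applies to the total. Calling these women the least dependent also goes too far: the gap is on one item, and their totals could be anywhere from 0 to 7. The SAP does not say that they are the likeliest to quit.

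**The subgroup harm should be put carefully.** Centre-mean replacement gives every replaced woman in a centre the same value, so all of them fall on the same side of the cut-off. The cut-off is not yet fixed in Section 4.7.3, so nobody can say in advance which women would be misclassified.

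**Conclusion.** The contradiction is certain on the text at hand: the key gives 1 to 10 and the SAP says 0 to 10. A first cigarette more than 60 minutes after waking has no listed score in 8.1 and no row in Table 4. This finding needs no assumption beyond a faithful reading of the PDF.

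The consequence is conditional and small. Only if the scoring code copied the omission would totals be wrong, by one point or by replacement with the centre mean. In the illustration of the second case, the treatment log odds ratio moved by no more than about a tenth of a standard error, as expected for a baseline covariate in a randomised comparison. The Fagerström coefficient weakened from about -0.25 to between -0.24 and -0.19. Those figures rest on assumed shares, means and coefficients. No primary or secondary conclusion is at risk. What could be wrong is the covariate itself, the baseline description and the Fagerström subgroup classification. Severity: minor.

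**What to change.** In Section 8.1, add a zero-scored answer to the first item for a first cigarette more than 60 minutes after waking. The SAP's own range supports this score. Add the matching row to Table 4, and for consistency a row for missing answers to that item.

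Before analysis, check that the database and scoring code hold this response as 0, and not as missing or merged into 31-60 minutes. Compute totals on the full 0 to 10 range. State in one sentence how a total is derived when an item is unanswered, so that centre-mean replacement under Section 4.4 applies only to women who did not answer.

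The cost is a few lines of SAP text and one check of the data and code. If the response was recorded, no new data are needed. If the form never offered that answer, these women cannot be told apart from the others, and the report should say so.
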